8. CRITERIA FOR EVALUATION AND ENDPOINT DEFINITION

An objective clinical response will be considered complete when gross inspection reveals no evidence of lesion(s) and will be considered partial when the product of bidimensional (perpendicular) millimeter measurements of the lesion or, if there are multiple lesions, the sum of the product of bidimensional measurements of all lesions

decreases by at least 50 percent. Lesions will be considered stable when the sum areas of all lesions combined increases by less than 25 percent or decreases by less than 50 percent. Disease progression will be defined as an increase of at least 25 percent in the total area of all lesions combined during treatment or as the appearance of any new lesion. Although we will collect histologic data on oral leukoplakia lesions, these data will not be included in the response assessments but will be available for exploratory analyses.

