1.2 Secondary Aims

1.2.1 The size, number, and appearance of oral IEN will be assessed and correlated with cancer risk. A $\geq 50\%$ reduction in the bidimensional measurements of IEN lesions is considered a treatment response. We hypothesize that patients with IEN lesions and LOH of the oral cavity will respond to erlotinib.

1.2.2 To examine toxicity associated with erlotinib. Our hypothesis is that patients with oral lesions will tolerate treatment with erlotinib.

1.2.3 To assess a panel of molecular markers for correlations with oral cancer development in our oral IEN patients. The markers will include (but are not restricted to):

1.2.3.1 EGFR, phospho-EGFR, TGF- α , ERK1/2, phospho-ERK1/2, AKT, phospho-AKT, COX-2, STAT3, phospho-STAT3, cyclin D1, HER2, Ki67, TUNEL, RAR- β , hTERT expression, E-cadherin, P-cadherin, vimentin, Src, phospho-Src, cytokeratin

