3. SUMMARY OF STUDY PLAN

The proposed study will be a double-blinded, placebo-controlled randomized study to evaluate the chemopreventive effect of erlotinib in a high-risk group of oral IEN patients. The trial will be conducted at five centers in the United States: M. D. Anderson Cancer Center, Memorial Sloan-Kettering Cancer Center, Emory University, the University of Chicago, and the University of Maryland. There will be two categories of high-risk patients in this study: (a) loss of heterozygosity (LOH) at 3p14 and/or 9p21 in the oral IEN of patients with a history of curatively treated oral cancer and (b) LOH at 3p14 and/or 9p21 plus at one other chromosomal region in the IEN of patients with no oral cancer history. The trial will randomize 150 patients--75 will receive erlotinib (150 mg po QD) and 75 will receive matched placebo (po QD). The trial period is 4.5 years (including one-year treatment)--2 years to complete accrual and 2.5 more years of follow-up (mean of the additional follow-up period from 1.5 to 3.5 years). A summary of the study schema appears below:

Once at the study site, informed consent will be obtained from willing participants, medical history will be obtained, oral lesions (if present) will be examined, blood samples will be taken, collection of archival tissue sample or biopsy of oral leukoplakia lesions for LOH analysis, and the epidemiologic and nutrition questionnaire (included in Appendix A) will be initiated. Patients classified with oral leukoplakia and LOH with or without a prior history of cured oral cancer will be eligible for inclusion in the study and will be randomized into one of two groups.

The primary endpoint of the trial will be the oral cancer-free survival in patients receiving erlotinib as compared with the control group. Multiple secondary endpoints will be assessed as outlined in Section 1.2.

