4. PARTICIPANT SELECTION

4.1 Inclusion Criteria

All the following conditions must be met before a patient can be included in the study:

4.1.1 Male or female patients with one of the following: (a) loss of heterozygosity (LOH) at 3p14 and/or 9p21 in the oral IEN of patients with a history of curatively treated oral cancer or (b) LOH at 3p14 and/or 9p21 plus at one other chromosomal region in the IEN of patients with no oral cancer history.

4.1.2 Participants must have confirmed diagnosis of oral IEN lesion with LOH. (Note: The initial screening biopsy of oral IEN lesion with LOH must be obtained within 12 months of study enrollment. If initial diagnostic biopsy for LOH is > 3 months prior to study enrollment, investigators may use clinical judgment to order an additional screening biopsy to assess histopathological changes).

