- h Study medication and pill diaries will be dispensed at randomization and during clinic visits at months 1, 3, 6 and 9
- i Unused study medication and completed pill diaries will be collected during clinic visits at months 1, 3, 6, 9 and 12
- j Review of pill diaries and compliance will be done during clinic visits
- k At final clinic visit
- l Every Q12 months (Months 24 and 36) during the follow-up period
- m For patients with visible oral leukoplakia lesions, quantitation of lesions, bidimensional measurements, and biopsy will be obtained. For patients with no visible oral leukoplakia lesions, a biopsy will be obtained at the site of the previous lesion biopsy or at mucosa adjacent to cancer resection.

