7.2 Baseline Testing/Pre-Study Evaluation

Following an introduction to the nature of the study, the study physician and research coordinator will evaluate each individual for enrollment. Baseline evaluations (**with the exception of the study questionnaire**) should be conducted within 30 days prior to initiating study treatment unless otherwise specified.

This will include:

- 7.2.1 Review of medical records for eligibility
- 7.2.2 Discussion of the risks, benefits, goals and limitations of the study and any alternate treatments that may be available with the subject.
- 7.2.3 Review of inclusion and exclusion criteria
- 7.2.4 Review of the informed consent process and form
- 7.2.5 Acquisition of informed consent and registration into study
- 7.2.6 Physical examination and examination of oral cavity (including baseline quantitation and bidimensional measurements of visible lesions)
- 7.2.7 Mucosal biopsies for histological analysis and LOH status.
Note: Biopsy will only be obtained if initial diagnostic biopsy of LOH is > 12 months prior to study enrollment or unavailable. If initial diagnostic biopsy for LOH is > 3 months prior to study enrollment,

investigators may use clinical judgment to order an additional screening biopsy to assess histopathological changes.

- 7.2.8 Symptom assessment and concomitant medication review
- 7.2.9 Study questionnaire (tobacco consumption, alcohol use, demographics, nutrition). Note: The research team will make every attempt to initiate the questionnaire within 30 days of beginning study treatment
- 7.2.10 Medical history (including smoking status and alcohol usage)
- 7.2.11 SGPT, SGOT, alkaline phosphatase, bilirubin, creatinine, sodium, potassium, magnesium, albumin, hemoglobin, hematocrit, platelet count, CBC with differential, WBC, and serum β HCG in females of childbearing potential (within 14 days of randomization).
- 7.2.12 Plasma drug trough assessment. This will be used as a baseline for each patient on which subsequent trough levels will be compared.
- 7.2.13 Family history of cancer
- 7.2.14 Blood collection for isolation of lymphocytes and biomarker analysis

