The Epidemiologic Questionnaire Database will contain entered data from completed epidemiologic and nutrition questionnaires. Hard copies of the epidemiologic and nutrition questionnaires will be filled out during an interview initiated at baseline and at the completion of the follow-up period. Participants at University of Chicago, Memorial Sloan-Kettering, Emory University – Winship Cancer Institute, and the University of Maryland will submit the original questionnaires to [name] at the following address to be edit checked and entered into the Epidemiologic Questionnaire Database:

[name]
U.T. M. D. Anderson Cancer Center
Department of Epidemiology
[name]
Houston, Texas 77030

The original will be stored in a locked file at M. D. Anderson Cancer Center following data entry.

Blood and Tissue Samples

If initial diagnostic tissue sample for LOH is > 12 months prior to study enrollment or unavailable, a biopsy sample will be taken from at least one existing lesion. Biopsy samples may be taken from all existing lesions at the discretion of the attending physician. The biopsies should be a minimum of 4-5 millimeters in diameter. If the entire lesion is excised at baseline, subsequent biopsies will be performed on normal appearing mucosa at the same site as clinically indicated. The biopsies will be partitioned for snap freezing and for fixation in 10% formalin immediately. Please note: Archival diagnostic tissue specimens obtained for LOH analysis will not be processed for snap freezing. All biopsy specimens (initial screening biopsy for LOH analysis and subsequent biopsy specimens) from Memorial Sloan Kettering Cancer Center, Emory University, University of Chicago, and the University of Maryland will be **ONLY** prepared for fixation (see Appendix G).

[figure not shown]
LOH investigations are performed on at least one sample taken (see “LOH Screening” section for details).

Blood - 10 cc's of blood (1-5cc EDTA tube and 1-5cc SST tube) will be drawn at each baseline, on-study and follow-up visit for analysis of routine laboratory parameters as listed in Section 7. 40 cc's of blood (3-10 cc heparinized tubes and 1-10cc EDTA tube) will be drawn at the pre-study blood draw for isolation of lymphocytes. 10 cc's of blood (1-10cc EDTA tube) will also be drawn at specified on-study visits for biomarker analysis and plasma trough levels.

Blood samples and biopsy specimens will be collected and shipped as detailed in Appendix G.

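### Complete response does not require a baseline lesion, so a lesion excised at baseline scores as a response, and a patient with no visible lesion at entry could score as one too

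*Combined protocol and SAP*

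**What the plan says.** Two places define lesion response.

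- Section 8: "An objective clinical response will be considered complete when gross inspection reveals no evidence of lesion(s". Partial response, stable disease and progression by area are all expressed as a percentage change in total lesion area. Progression can also be declared when a new lesion appears. Histology is kept out of the response assessment.
- Section 1.2.1: a fall of 50% or more counts, in that a "reduction in the bidimensional measurements of IEN lesions is considered a treatment response".

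Other sections bear on who has a lesion to respond.

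- Section 3 says that "oral lesions (if present) will be examined", so a lesion need not be there at the baseline examination.
- Section 7.2.6 requires the oral examination at baseline, "including baseline quantitation and bidimensional measurements of visible lesions".
- Section 7.7, under Blood and Tissue Samples: "If the entire lesion is excised at baseline, subsequent biopsies will be performed on normal appearing mucosa at the same site as clinically indicated". The patient stays on study.
- The eligibility criteria (Section 4.1) ask for a confirmed lesion with LOH, shown by biopsy. They do not ask for a visible or measured lesion at randomization.

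No section defines a response-evaluable set. Section 12.2 states an intent-to-treat analysis, but under the primary endpoint.

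**The concern.** Complete response is the only response category in Section 8 that does not compare follow-up with baseline. It describes how the mouth looks at one visit. Two kinds of patient can meet it without any effect of study drug: those whose lesion was cut out at baseline, and those who had no visible lesion when they entered.

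Lesion response belongs to the first secondary aim (Section 1.2.1). Section 2.1 gives the relation between lesion response and cancer outcome as something the trial will allow to be assessed, and Section 8.2.1 plans to correlate lesion size with reduction in cancer risk. False responses would raise the response rate in both arms and narrow the difference between them. In the correlation with cancer they would place surgical removal, or having no lesion, in the same category as regression on drug. The documents do not show which way that would push the correlation.

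**Working it through.** **Step 1. Apply the two rules to each kind of patient.** Let A0 be the total lesion area at baseline and A1 the area at follow-up. The percentage reduction is (A0 − A1)/A0.

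| Patient | Section 8 | Section 1.2.1 |
|---|---|---|
| Lesion measured, left in place, gone at follow-up | Complete response | 100% reduction: response |
| Lesion measured, then wholly excised at baseline | Complete response | (A0 − 0)/A0 = 100%: response |
| No visible lesion at entry, none at follow-up | Complete response on the literal wording | 0/0: undefined |

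In the second row both rules give the wrong answer. In the third row Section 8 taken literally gives a complete response, and Section 1.2.1 gives no answer. With A0 = 0, every Section 8 category that rests on percentage change is also undefined. Only complete response and progression by new lesion can then be assigned at all.

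**Step 2. Effect on a comparison of response rates.** The plan gives no response rate, power or test for response, so there is no figure to reproduce. Let r be the true response rate among patients with a lesion left in place, and p the affected share, taken as equal in the two arms because of randomization. If all randomized patients are in the denominator and the affected ones count as complete responses:

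- observed rate = p + (1 − p)r
- observed difference = (1 − p)(r_E − r_P), where E is erlotinib and P placebo

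The factor (1 − p) does not depend on the rates chosen. It also holds if some affected patients are lost to new-lesion progression, provided that the proportion is the same in both arms.

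**Step 3. Illustration.** All rates and all values of p are assumptions. Only the 75 patients per arm come from the protocol (Section 3). Power is for a two-sided 5% test of two proportions by normal approximation, with pooled variance under the null. Assumed true rates are 10% placebo and 30% erlotinib.

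| p | Placebo | Erlotinib | Difference (points) | Power, all 75 per arm | Power, only the 75(1 − p) per arm with a lesion |
|---|---|---|---|---|---|
| 0 | 10% | 30% | 20 | 87.2% | 87.2% |
| 10% | 19% | 37% | 18 | 69.3% | 83.5% |
| 20% | 28% | 44% | 16 | 53.3% | 78.9% |
| 30% | 37% | 51% | 14 | 40.7% | 73.3% |
| 50% | 55% | 65% | 10 | 23.8% | 58.4% |

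For p = 30%: 0.30 + 0.70 × 0.10 = 0.37 and 0.30 + 0.70 × 0.30 = 0.51.

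Other assumed rates follow the same pattern. With 20% v 50%, the 30-point difference becomes 24 points at p = 20% (36% v 60%) and 15 points at p = 50% (60% v 75%). In every case computed, leaving the affected patients out of the denominator costs less power than counting them as responders.

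**The case against.** The strongest reply is that Section 8 grades a response that has already occurred, and that Section 1.2.1 says what a response is: a reduction in measurements. A patient who starts with nothing to measure has no reduction, and a sensible analyst would leave that patient out. This stands in part. For patients with no visible lesion at entry, the plan does not say that they will be counted, so the claim is that they could be. It does not help with excised lesions, which show a 100% reduction under Section 1.2.1 itself.

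A reader might also infer from two other passages that affected patients are many. Neither shows it. Section 4.1.2 accepts an LOH biopsy taken up to 12 months before enrollment, but a biopsied lesion may still be there. Footnote m in Section 7.1 gives a biopsy rule for patients without visible lesions at months 3 and 12, but that group includes lesions that regressed on study. Excision at baseline may itself be limited, since a new baseline biopsy is taken mainly when the diagnostic sample is too old or unavailable. The number affected is simply not known.

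Finally, no between-arm test of response is specified, and Section 8.2.1 speaks of lesion size rather than response category. That is correct, and it limits the weight of the power figures. But a change in size caused by excision is no more a drug effect than a response label is, so the correlation with cancer risk still needs these patients separated.

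**Conclusion.** The point holds. For a lesion measured and then wholly excised at baseline, the stated rules themselves give a wrong result. For a patient with no visible lesion at entry, the plan leaves open a wrong result that its literal wording supports. A reader might infer that every patient without a lesion will be reported as a responder, but the documents do not go that far.

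The size that can be defended is the dilution factor (1 − p), given equal shares in the two arms and all randomized patients in the denominator. The value of p, the response rates and the power figures are illustrative. A reader might also infer that erlotinib would be favoured or that the main result is at risk. Neither follows. With equal shares the error inflates both arms and narrows the difference. The primary endpoint, time to histologically confirmed oral cancer, does not use the response rule, so its stated 85% power is unaffected. This is a defect in a secondary endpoint that should be corrected.

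**What to change.** Amend Section 8 before unblinding:

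- Restrict complete response, partial response and stable disease to randomized patients with at least one visible, bidimensionally measured baseline lesion that was not wholly excised at or before the start of treatment.
- Define complete response as disappearance of all such lesions.
- Class all other patients as not evaluable for response, and still record new lesions in them as progression.
- Align Section 1.2.1 with this definition.

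The baseline measurements (Section 7.2.6) and the numbered lesion diagrams (Section 8.2.1) already exist. What must be added is a recorded flag for whole-lesion excision and its date. No re-measurement after excision is needed, and the protocol does not provide for one. The cost is that one extra data item and a smaller denominator for response.

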8.4 Off-Study Criteria

Patients may go off-study for the following reasons:

- The protocol intervention and any protocol-required follow-up period is completed
- Diagnosis of cancer
- Lost to follow-up
- Withdraw consent
- Death.

Patients that have been placed off study will be asked to return to the study site for an early termination visit according to the schedule of events (Section 7.1).

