12.2 Analysis of Primary Endpoint

The primary endpoint of the study is cancer-free survival defined as time from randomization to the development of histologically confirmed oral cancer. All patients will be analyzed on an intent-to-treat basis (i.e., as randomized). Patients lost to follow-up due to refusal or death from other causes will be censored at their time of last follow-up. The distribution of time to oral cancer development will be estimated by the Kaplan-Meier method. For randomization purposes, eligible patients will be stratified (1) by prior oral cancer status (no prior oral cancer versus prior oral cancer) and (2) broadly by registration site (M. D. Anderson versus non-M. D. Anderson site). Within each stratum, Pocock-Simon dynamic allocation method will be applied to achieve balanced randomization with respect to potentially important factors including current, former and never smoking. Patients will be randomized into the erlotinib arm or the placebo arm with equal probability. Stratified log-rank test will be used to compare cancer-free survival among treatment groups. The Cox (proportional hazards) regression model will be used to incorporate potential prognostic factors and treatment assignment as covariates. Details of the assumptions used for the sample size calculation are listed below.

1. The study has a 2-year period to accrue 100 oral IEN/prior cancer and 50

IEN-alone patients, with an additional 2.5-years follow-up. The total study duration is 4.5 years.

2. The anticipated yield of LOH screening (described earlier) will be approximately 66% in the IEN/LOH-cancer history group and 28% in the IEN/LOH-alone group. Assuming accrual rates of 60% (eligible, cancer history) and 45% (eligible, no cancer history), we will need to screen a total of 253 oral IEN patients with and 365 (accounting for year-2 accruals who were screened, eligible, and did not volunteer in year 1) oral IEN patients without a history of curatively treated oral cancer at all four participating centers in order to reach our total accrual goal.
3. Time-to-oral cancer development follows an exponential distribution. Based on the data described earlier, 65% of the patients with IEN/LOH associated with curatively treated oral cancer will develop oral cancer in three years, and 35% of the IEN/LOH-alone patients will develop oral cancer in three years.

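### As Section 8 is written, a lesion that shrinks while turning malignant, or that is removed on study, can be scored as a treatment response

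*Combined protocol and SAP*

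**What the plan says.** Section 8 gives four categories. Response is complete when no lesion is seen on gross inspection. It is partial when the area product, or the sum of products over several lesions, "decreases by at least 50 percent". For the middle category, "Lesions will be considered stable when the sum areas of all lesions combined increases by less than 25 percent" or falls by less than half. For the last, "Disease progression will be defined as an increase of at least 25 percent in the total area of all lesions combined during treatment"; a new lesion also counts. The section then closes the door on biopsy findings: "Although we will collect histologic data on oral leukoplakia lesions, these data will not be included in the response assessments". They are kept for exploratory use.

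Section 1.2.1 repeats the area rule: a 50% or greater "reduction in the bidimensional measurements of IEN lesions is considered a treatment response". Sections 1.2.1 and 8.2.1 plan to correlate lesion measurements with cancer risk, and Section 2.1 names the link between lesion response and cancer outcome as something the trial will assess.

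Cancer is handled separately. Section 12.2 defines the primary endpoint as "time from randomization to the development of histologically confirmed oral cancer". Section 8.4 lists a cancer diagnosis among the reasons for leaving the study and adds: "Patients that have been placed off study will be asked to return to the study site for an early termination visit". Under Sections 7.4.1 and 7.4.3, visible lesions are measured and biopsied together at month 3 and at month 12 or early termination.

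**The concern.** A patient can fail on the primary endpoint and count as a success on the secondary one, from the same lesion at the same visit. A removed lesion can likewise be read as a drug response, because inspection cannot tell regression from excision. This point is about events after randomization, not lesions already absent or excised at baseline.

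Two things are at stake. One is the lesion response rate: if erlotinib prevents cancer as the plan assumes, about twice as many placebo as erlotinib patients have a first-year cancer, so any such misscoring is uneven by arm. The other is the response-cancer correlation, where some responders would be patients whose cancer was already present when response was scored.

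**Working it through.** **1. The plan's own figure.** The documents give no figure for lesion response. The figure to reproduce is the 85% power in Section 12.2, which checks the hazards used below.

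- Hazards from the 3-year rates: −ln(1 − 0.65)/3 = 0.3499 and −ln(1 − 0.39)/3 = 0.1648 with prior cancer; −ln(1 − 0.35)/3 = 0.1436 for control in IEN alone. The stated treatment value there is 0.0676. Both ratios are 0.471, against 0.47 stated.
- Simulation with 10,000 replications: 100 + 50 patients, uniform 2-year accrual, 10% uniform loss, and a stratified log-rank test at years 2.5, 3.5 and 4.5 at two-sided 0.0005, 0.014 and 0.045. Power was 86.0% (86.1% with four strata), type I error 0.0495, and about 69 events were expected. The stated power is reproduced.

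**2. The rules applied to two patients.**

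- *Same-visit cancer.* A lesion goes from 20 × 10 = 200 mm² to 12 × 8 = 96 mm² at month 3. 96/200 = 0.48, a 52% decrease. The biopsy at that visit shows invasive cancer. Section 12.2 makes this a primary event; Section 8 makes it a partial response. If the cancer is instead held to be no longer a leukoplakia, it drops out of the summed area and the total falls further. Neither reading gives progression.
- *Removal.* A patient's only lesion is removed on study before a measurement visit. Nothing is seen on inspection, so Section 8 gives a complete response. This could arise at the early termination visit after a cancer, or at a scheduled visit of a patient who stopped the agent for alternative therapy and returns as Section 8.3 asks. The documents do not say whether removal precedes the visit, and have no rule if it does.

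**3. Patients exposed to the gap.** Expected first-year cancers are Σ n × (1 − exp(−λ × 1 year)), with 50 prior-cancer and 25 IEN-alone patients per arm:

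- Placebo: 50 × (1 − e^−0.3499) + 25 × (1 − e^−0.1436) = 14.76 + 3.34 = 18.1 of 75, or 24.1%.
- Erlotinib: 50 × (1 − e^−0.1648) + 25 × (1 − e^−0.0676) = 7.60 + 1.63 = 9.2 of 75, or 12.3%.
- Difference: (18.11 − 9.23)/75 = 11.8 points.

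By month 3 the counts are 5.1 and 2.4. All are upper bounds on exposure: a cancer at a new site already scores as progression, some patients have no measurable lesion, and losses are ignored.

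**4. Effect on a response rate.** Let p be the first-year cancer risk, r the response rate in cancer-free patients and q the share of cancer patients scored as responders. Observed response = (1 − p)r + pq. With q equal in both arms, the erlotinib-minus-placebo difference falls by 11.8 × q points relative to q = 0. Both r and q are assumptions; the documents give neither.

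| q | r = 10% placebo, 30% erlotinib | r = 20% in both arms |
|---|---|---|
| 0 | 7.6% vs 26.3%: +18.7 | 15.2% vs 17.5%: +2.4 |
| 0.5 | 19.7% vs 32.5%: +12.8 | 27.2% vs 23.7%: −3.6 |
| 1 | 31.7% vs 38.6%: +6.9 | 39.3% vs 29.8%: −9.5 |

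Each cell gives placebo vs erlotinib, then the difference in points from unrounded values. With unequal q, the shift against erlotinib is 24.1 × q(placebo) − 12.3 × q(erlotinib). It changes sign only if q on erlotinib exceeds 24.1/12.3 = 1.96 times q on placebo.

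**The case against.** The strongest reply is that the separation is deliberate. Section 2.1 reports that response did not correlate with cancer in an earlier large retinoid trial, and this trial wants to look again. A responder who develops cancer is then a finding, and defining cancer as non-response makes the correlation partly circular. That stands, and the fix has to deal with it. Leaving dysplasia grade out of response is likewise a legitimate choice.

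The reply also has force on size. Section 12 specifies no between-arm test of response. The values of r and q are assumed. About 82% of the expected first-year cancers (22.4 of 27.3) fall in the prior-cancer cohort, and the protocol provides for patients with no visible lesion, including biopsy beside a cancer resection. Scoring cancer as non-response has its own tilt: the q = 0 row shows +2.4 points for erlotinib with no true lesion effect.

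Some stronger readings are tempting but not supported:

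- That response rests on area alone. Complete response is by inspection, and any new lesion is progression.
- That a resected cancer will be called a complete response. This needs removal before the visit and no other visible lesion. Section 8.4 only asks patients to attend, Section 11 prefers the visit within 14 days of leaving the study, and Section 8.3 exempts oral cancer patients from the remaining visits.
- That a malignant lesion growing by 15% (200 to 230 mm²) inflates response. It is scored stable, which is not a response.

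What the reply does not remove is the rule itself: an existing lesion that halves in area with cancer on biopsy is a partial response, with no assumption about surgery or timing.

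**Conclusion.** The point holds for the secondary response endpoint and its correlation with cancer. Section 8 sets a literal rule, and no other section overrides it for cancer in an existing lesion or for removal on study. Followed as written, it can give a wrong classification.

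At most about 18 placebo and 9 erlotinib patients are exposed through first-year cancers. The possible shift is up to 11.8 × q points against erlotinib: 1.2 points at q = 10%, 5.9 at 50%. This assumes the plan's hazards, the planned treatment effect and a similar q in both arms. Removals without cancer are not counted, because the documents give no rate for them.

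A reader might infer that the trial's main result is compromised, or that the response comparison would be reversed. The first is wrong: the primary endpoint counts cancer separately, so the 85% power stands. The second depends on an unknown q and on a comparison the plan does not specify.

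**What to change.** Amend Section 8, before unblinding, to state three things:

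- (a) For the response rate, histologically confirmed oral cancer on or before the response assessment counts as progression, and so as non-response, whatever the lesion area. Dysplasia grade stays exploratory.
- (b) A measurement taken after removal of a lesion on study cannot give a complete or partial response. The date of any removal is recorded.
- (c) The correlation of response with cancer uses response at one fixed visit, month 3 or month 12, among patients cancer-free at that visit, and relates it only to cancers diagnosed afterwards. This keeps rule (a) from making the correlation circular.

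The cost is a few sentences, some programming and one added data item; cancer diagnoses and biopsy results are already collected. There are three downsides. The reported response rate will be slightly lower. It becomes partly a composite with cancer, so a drug that only prevents cancer would show a small response advantage, about 2 points if true response is 20% in both arms; the report should say so. The landmark correlation will include fewer patients.
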